Over the last decade, researchers have begun to examine the hypothesis that resilience can be enhanced. In fact, the development of interventions designed to promote resilience in other populations has led to positive outcomes.¹³⁵ Research on adults facing cancer,^{138,139} PTSD,^{140,141} anxiety disorders,¹⁴² diabetes,¹⁴³ and other illness and injury types¹⁴⁴ has demonstrated substantial gains on measures assessing degrees of resilience. More specifically, a number of the skill-deficits often associated with non-resilient profiles have shown significant improvement following resilience-promotion interventions. Measures of emotional well-being consistently improve, while indicators of psychological distress decline.^{138,142,144,145} Furthermore, measures of injury/illness adjustment often show gains.^{138,140,143,146} Improvement in ability levels on measures of problem solving, communication, and stress reduction are also frequently noted.^{138,140,142-144} Moreover, health-behaviors and functional abilities have also improved following treatment.^{140,143,144}

Resilience and TBI: Given the long-term challenges of TBI, many authors have asserted the critical need for developing a resilience-promotion approach to treatment in brain injury rehabilitation settings.^{91,92,95,147} In a recent study, VCU researchers⁹³ investigated the relationship between resilience, emotional distress, and participation in a treatment-seeking, outpatient sample

with mild, moderate, and severe TBI. The investigators found a relationship between resilience, emotional adjustment, and depressive symptoms. Lower levels of resilience were associated with greater psychological distress. The authors concluded that interventions that successfully target resilience are likely to benefit emotional well-being. In a series of recent studies, Losoi and colleagues¹⁴⁸⁻¹⁵⁰ and Sullivan and colleagues¹⁵¹ examined postinjury resilience in patients with mild TBI. Greater resilience was associated with fewer post-concussion symptoms and better quality of life. Sullivan, in a later systematic review, reaffirmed that higher levels of resilience were associated with fewer post-concussion symptoms.¹⁵²

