Additional quality control procedures will be implemented for booster sessions with each

therapist. As indicated in the Intervention section, booster sessions are person-centered and thereby

highly individualized. Audio-recordings will be made for the three booster sessions and reviewed

with [name] to ensure that key areas are covered as outlined in the manual. Every six months

thereafter, quality control procedures will be repeated.

Data collection procedures: Demographic, injury severity, and history information will be

collected at baseline using TBIMS standard procedures. For RAI and RAI+ participants, outcome

measures will be obtained prior to treatment (baseline) and following completion of the RAI.

Outcome measures for RAI+ participants will be obtained at the start and completion of the booster,

and six months following completion of the booster sessions. Measures for RAI participants will be

obtained at three, four, and nine months post-RAI treatment. Data collection will occur within the

same timeframe for both RAI and RAI+ participants as outlined in the figure that follows.

Project timeline: The major activities for the research project are sequentially delineated in the

Plan of Operation section.

E. Data Analysis

Descriptive statistics (e.g., means, standard deviations, proportions) will be calculated for all

measures at designated time intervals. Analyses will be performed using the university licensed

statistical program SAS v.9.3 (© 2002- 2010; SAS Institute Inc.; Cary, NC). The following table

provides a description of major statistical analysis procedures, emphasizing priority areas related to

research hypotheses. Information is provided regarding statistical hypotheses, statistical methods,

power analysis and sample size estimates. Analyses evaluating the RAI+ are based on the intent-to-

treat principle if drop-out is assumed as missing at random or missing completely at random.

Hypothesis 1 – Primary: Participants receiving the booster (RAI+ group) will report higher levels of resilience in comparison to individuals in the standard RAI group.

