Statistical Methods: A linear mixed-effects model will be used to model the CD-RISC scores over time for the RAI and RAI+ groups. The model will include fixed-effects for time at RAI+Booster initiation, conclusion, and long-term follow-up (e.g. 5, 6, and 11 months), group (RAI or RAI+) and the interaction between group and time. The model will also adjust for fixed-effects for injury severity, time postinjury, and education. Within-subject correlations in the CD-RISC scores over time will be modeled using a spatial power covariance pattern structure. Specific contrast statements will be used to test for a difference in the CD-RISC change scores between the treatment groups at both RAI+Booster initiation and conclusion as well as RAI+Booster initiation and long-term follow-up at a significance level of .05.

Power Analysis: Data obtained by our group indicated that the mean CD-RISC increased from a baseline value of 21.1 units to a mean of 28.4 units post-treatment (Difference=7.3), followed by a decline to 25.5 at the 3-month follow-up (Difference=2.9), with a standard deviation (SD) of the change score equal to 5.0. Considering a conservative SD of 6.0, this study will require 138 participants (n=69 per group) using a two-sample t-test performed at the 0.05 significance level to achieve 80% power. This effect translates to an effect size d=2.9/6.0=0.48, which is typically considered a moderate effect size.

Hypothesis 2: Participants in the RAI+ group will show better adjustment and lower levels of emotional distress as compared to persons in the standard RAI group.

Statistical Methods: Separate mixed-effects models, similar to that outlined in the methods for Hypothesis 1, will be used to model the responses for the MPAI-4 Adjustment Index and the BSI-18 GSI scores over time for each group. Specific contrast statements will be used to test the hypotheses of interest, each assuming a significance level of .05. Using a similar 40% decrease between the baseline to post-treatment values observed in our pilot study, we would expect the RAI+ to ameliorate declines in the MPAI-4 Adjustment and BSI-18 GSI scores by 1.7 and 2.6 points, respectively. Considering a conservative SD of 7.0, the 138 participants enrolled would provide power of 29% and 58% for the two outcomes, if analyzed by a two-sample t-test at the 0.05 level.

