Using randomization tables, participants will be assigned to either of two treatment groups: (1) Resilience and Adjustment Intervention (RAI), or (2) RAI+. After randomization, a second appointment will be scheduled. All participants will begin the 7-session treatment during their second appointment. The intervention consists of seven 60-minute sessions scheduled over seven weeks (see attached RAI Implementation Manual). During the first session, participants will receive an empty loose leaf binder to store and organize completed self-assessments, reading materials, and homework assignments from each session. They will be asked to review materials and complete worksheets between sessions. The intervention will be implemented by experienced, licensed therapists (Ph.D. level Interventionists). Participants will be randomly assigned to one of the therapists.

The RAI and RAI+ groups will both complete the post-treatment measures immediately after the seventh treatment session and then 3, 4, and 9 months later. Data collection at 3, 4, and 9 months post-treatment will be completed inperson, unless the participant requests to complete via phone.

Furthermore, the RAI+ group will complete 3 booster sessions, spaced approximately 7-10 days apart, beginning 3 months after completion of the seventh treatment session (booster sessions will occur between the 3 and 4 month data collection described above).

Data will be analyzed to identify any therapist effects, as well as treatment effects. For the RAI and RAI+ groups, demographic, injury severity, and history information will be collected at intake using standard procedures and protocols. All participants will complete the 4 outcome measures (Connor-Davidson Resilience Scale, CD-RISC; Mayo Portland Adaptability Inventory-4, MPAI-4; 13 Item Stress Test; and Brief Symptom Inventory-18, BSI-18) at 5 time points (intake, post-treatment, and 3, 4 and 9 month follow-up).

The RAI is not a standard of care at VCU. Both the RAI and the RAI+ are experimental interventions. Any information collected during the intervention sessions (e.g., questionnaires, lists generated) is part of the experimental intervention, not part of the research data.

7. * The IRB only reviews research activities, so indicate for each of the study activities described in the question above or in the protocol which activities are:

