The research staff will pay particular attention to and attempt to minimize any risks that may occur as a result of participation in this study. For this study, risks to subjects are less than minimal. Potential risk is mitigated in several ways. Research staff who collect the data are well trained and very familiar with the population. The de-identification and coding process is the safeguard in place to minimize risk of breach in confidentiality. And, research activities are completed in a private clinical setting to minimize risk related to breach in privacy.

- 3. * Describe any potential risks or harms to a community or a specific population based on study findings (e.g. information that could be stigmatizing or derogatory): None.
- 4. Where appropriate, discuss provisions for ensuring necessary medical, professional, or psychological intervention in the event of adverse events to the subjects:

The PI is on call during each interview is responsible for monitoring the status of enrolled participants and addressing urgent situations. When concerns arise, the PI is contacted immediately to make a clinical decision regarding the need for further evaluation, treatment, or referral.

- 5. * Describe criteria for when the investigator would withdraw an individual participant from the study; such as safety or toxicity concerns, emotional distress, inability to comply with the protocol, etc.: If the participant experiences significant emotional distress during the intervention sessions, the Interventionist may recommend study withdrawal in order for the person to seek a more appropriate and intensive treatment for mental health problems. Referrals will be made to the VCUHS Neuropsychology Clinic located at Stony Point. If the participant's emotional difficulties improve, they may return to complete the study.
- 6. * Summarize any pre-specified criteria that would trigger the investigator/sponsor/monitoring committee to stop or change the study protocol due to safety concerns: None.

Data and Safety Monitoring

Data and safety monitoring is a system for checking the study's data at regular intervals over the study period to identify and address issues that could affect the safety of research participants. This requirement is in accordance with 45 CFR 46.111.

The purpose of data and safety monitoring plan is to set forth study team procedures for monitoring/addressing:

- Participant safety (physical, psychological, etc.)
- Data validity

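### The distress rule allows withdrawal from the study, not only from sessions, so month-6 and month-11 scores could be lost through it from RAI+ alone; the size cannot be determined and is probably small

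*Combined protocol and SAP*

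**What the plan says.** The rule stands in the IRB application, Risks, Discomforts, Potential Harms and Monitoring, item 5, which asks when a participant would be withdrawn from the study. The answer is: "If the participant experiences significant emotional distress during the intervention sessions, the Interventionist may recommend study withdrawal", so that the person can seek other care. It adds: "If the participant's emotional difficulties improve, they may return to complete the study". No time limit or visit is attached to the return, and stopping sessions is not distinguished from stopping outcome assessment.

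The schedule is in Study Procedures, item 6. Both arms have the seven core sessions and are assessed at post-treatment and then 3, 4 and 9 months later. In addition, "the RAI+ group will complete 3 booster sessions, spaced approximately 7-10 days apart, beginning 3 months after completion of the seventh treatment session". The boosters fall between the 3- and 4-month assessments.

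In the grant proposal, E. Data Analysis, Hypothesis 1, those three assessments are months 5, 6 and 11. Contrasts will "test for a difference in the CD-RISC change scores between the treatment groups at both RAI+Booster initiation and conclusion", and likewise between initiation and long-term follow-up. Within-subject correlations "will be modeled using a spatial power covariance pattern structure". The analysis follows the intent-to-"treat principle if drop-out is assumed as missing at random or missing completely at random".

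**The concern.** Distress during a session can trigger the rule only in someone who is having sessions. During the core programme that is both arms. Between months 5 and 6 it is RAI+ only, and both primary contrasts start at month 5. Someone withdrawn in that window already has a month-5 score; the month-6 and month-11 scores are the ones at risk.

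The reason for loss may be related to the outcome. The grant proposal's review, under Resilience and TBI, reports: "Lower levels of resilience were associated with greater psychological distress". That is a cross-sectional association in an outpatient sample and says nothing about change, but it makes a link plausible. If the distress arises in a booster and goes with a fall in resilience that the month-5 score does not predict, the missing-at-random condition fails for those participants, and the RAI+ mean is estimated without some of its lower scores. If withdrawal depends only on the observed month-5 score, the condition holds and the mixed model deals with it.

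**Working it through.** **The plan's own figure.** With d = 2.9/6.0 = 0.48, two-sided 0.05 (sidedness is not stated; assumed) and 80% power, the exact two-sample t calculation gives 68.2, hence 69 per group and 138 in total, with power 80.5%. The inflations also reproduce: 138/(1 - 0.28) = 191.7, so 192 (IRB application, Study Population, item 3), and 138/(1 - 0.10) = 153.3, so 154 (grant proposal). Neither attrition allowance is split by arm or reason.

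**Exposure to the rule, from the schedule.**

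| Period | Sessions in RAI | Sessions in RAI+ | Place in the primary contrasts |
|---|---|---|---|
| Core programme | 7 | 7 | before both |
| Post-treatment to month 5 | none | none | before both |
| Month 5 to 6 | none | 3 boosters | inside both |
| Month 6 to 11 | none | none | inside the long-term contrast |

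This step needs no assumption.

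**Power.** Losing 1, 3, 5 or 7 of 69 from RAI+ alone gives 80.2%, 79.6%, 78.9% or 78.3%. Any concern is about bias, not power.

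**Bias: inputs.** The CD-RISC SD is 7.8 (prior trial, RAI arm, 3-month follow-up). The prior decline of 2.9 is given "with a standard deviation (SD) of the change score equal to 5.0"; the planning SD is 6.0. My assumptions: a share p of 2%, 5% or 10% of RAI+ is lost (69p = 1.4, 3.5, 6.9, so about 1, 3 and 7 people), and those lost would have averaged 1 SD (7.8 points) below the arm mean at month 6.

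**Correlation.** Taking the change SD as spanning the three months after treatment, with equal SDs at both ends:

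- r over three months = 1 - SDchange²/(2 × 7.8²). With 5.0: 1 - 25/121.68 = 0.795. With 6.0: 1 - 36/121.68 = 0.704.
- Under spatial power the one-month r is the cube root: 0.926 and 0.890.

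**Formula.** Without the lost scores, the observed RAI+ mean at month 6 is too high by p/(1-p) × 7.8. A likelihood analysis takes back r times the corresponding shift at month 5.

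- Case A, lost participants correspondingly low at month 5 (r SD below the mean): bias = p/(1-p) × 7.8 × (1 - r²).
- Case B, lost participants average at month 5, so that the fall is wholly new: nothing is taken back, and bias = p/(1-p) × 7.8.

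| Share lost | p/(1-p) | A, r = 0.926 | A, r = 0.890 | B |
|---|---|---|---|---|
| 2% | 0.0204 | 0.02 | 0.03 | 0.16 |
| 5% | 0.0526 | 0.06 | 0.09 | 0.41 |
| 10% | 0.1111 | 0.12 | 0.18 | 0.87 |

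For example, at 10% with r = 0.890: 0.1111 × 7.8 × (1 - 0.890²) = 0.18. Simulated trials (69 per arm, no true effect, 20,000 per cell) agree with every cell to about 0.01.

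Against 2.9 points, case A runs from about 1% (0.02/2.9) to 6% (0.18/2.9) and case B from about 5% (0.16/2.9) to 30% (0.87/2.9). The top of case B is extreme. The one-month change SD is 7.8 × √(2(1-r)) = 3.0 or 3.7, so a 7.8-point fall in one month is 2.6 or 2.1 of those SDs.

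**Month 5 to 11, nobody returning.** Multiply by r⁵ (0.68 or 0.56): case A gives about 0.02 to 0.10 points.

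**The case against.** The case for leaving this alone is substantial.

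- *The loss is several steps from certain.* Distress must be significant and arise in a session, the recommendation is discretionary, the participant must accept it, and return is allowed. The IRB application rates risk as less than minimal and expects discomfort not to outlast the session (Behavioral Intervention/Task Details, item 4). Anyone reaching the boosters has already had seven sessions under the same rule. All this stands and favours the low end of the range.
- *The default is full assessment.* Study Procedures, item 6, has all participants completing the outcome measures at five time points, and Data Retention makes withdrawal of data a separate step on the participant's request. This stands as the default, but neither passage expressly covers someone withdrawn from the study.
- *The consent form may settle it.* The consent form, the contingency protocol and the phone follow-up script are listed but were not available for this review, so their silence cannot be assumed. This is why the fix starts with a check. The written rule still says study withdrawal.
- *Drop-out reasons are already reported*, in the Plan of Evaluation and the Data Safety Monitoring Plan. True, but a recorded reason does not supply a score.
- *The direction is assumed.* Withdrawal is meant to lead to other care, which could improve later scores. This stands, especially for month 11.

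A reader might infer that data will be missing only in RAI+, or that the primary result is tilted towards RAI+. The documents support neither. RAI participants can be lost in the same window for other reasons, and the one-sidedness concerns this rule alone.

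**Conclusion.** The point holds as a matter of wording and schedule. The rule withdraws people from the study, and between months 5 and 6 it can act only on RAI+, inside both primary contrasts, for a reason that may be related to resilience. Whether missing at random then fails depends on whether the distress reflects something that the month-5 score does not carry.

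The size is not determinable, because no rate of distress withdrawal is given. With 2-10% of RAI+ lost and a 1 SD lower month-6 score, both assumed, the month 5-to-6 bias is about 0.02-0.18 points if month-5 scores were correspondingly low, and about 0.16-0.87 if they were average. The low end is the more plausible. The direction is likewise an assumption. This is a cheap, low-priority improvement, not a threat to the trial's conclusion.

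**What to change.** Check first whether the consent form already provides for questionnaires after sessions stop. If not:

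- Leave the clinical decision and the referral as they are, and separate stopping sessions from leaving the study.
- State that anyone who stops sessions is still offered the scheduled 3, 4 and 9 month questionnaires, by phone if preferred, unless they withdraw consent, and is analysed in the assigned arm.
- Record the date on which sessions stopped and report it, with the reason, by arm.

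The cost is a short amendment and a check of the consent wording. The visits, the phone option (Study Procedures, item 6) and a payment for each completed assessment (Compensation, item 1) are already planned. The downside is a few extra contacts with people who stopped because of distress.

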8 DOCUMENTS

Click Continue below to go to the next section

Populations with Special Considerations

1. * C	heck all participar	nt groups that will be either						
a	Specifically included in this study or							
b) Discernable in th	Discernable in the research data/specimens.						
(\$	Selections will brai	nch)						
	Children							
C	Emancipated m	inors						
C	Wards of the St	ate						
~	Pregnant wom	en or fetuses						
C	Neonates or Po	st-delivery Materials						
C	Prisoners							
~	Decisionally In	npaired Adults						
~	VCU Health Sy	stem or VCU Dental Care patients						
~	VCU / VCUHS	students or trainees						
~	VCU / VCU Hea	Ith System employees						
C	Individuals with	limited English proficiency						
	Active military p	ersonnel						
	Student populat	ions in K-12 educational settings or other learning environments						
C	Members of a fe	ederally recognized American Indian and Alaska Native tribe						
C	None of the Abo	ove						
_		owing categories that apply to this research:						
×	45 CFR 46.204	Research involving pregnant women or fetuses.						
	46.205(a) and (b)	Research involving neonates of uncertain viability.						
	45 CFR							
L	」 46.205(a) and (c)	Research involving nonviable neonates						
C] 45 CFR 46.205(d)	Research involving viable neonates.						
C	45 CFR 46.206	Research involving, after delivery, the placenta, the dead fetus, or fetal material.						
C	45 CFR 46.207	Research not otherwise approvable which presents an opportunity to understand, prevent, or alleviate a serious problem affecting the health or welfare of pregnant women, fetuses, or neonates.						
		tions for student populations: be research participants in the study:						
~	VCU Students							
~	K-12 Students							
~	Parents/Guard	ians of Students						
~	Teachers							

Administrators

4. If applicable, describe any alternative activities for students (including VCU students) who choose not to participate in the research.

5. * Describe how the study will minimize the possibility of coercion to participate.

The purpose of the study is to evaluate the efficacy of a structured, curriculum-based intervention to promote postinjury resilience and adjustment. The study is not specifically focused on students, but there is no reason to exclude those who are students from participating. This is a survey study, and research personnel conducting informed consent will emphasize the voluntary nature of participation.

6. Additional considerations for VCU/VCU Health System employees:

* Describe how the study will minimize the possibility of coercion to participate.

The purpose of the study is to evaluate the efficacy of a structured, curriculum-based intervention to promote postinjury resilience and adjustment. The study is not specifically focused on VCU employees, but there is no reason to exclude those who are employees from participating. This is a survey study, and research personnel conducting informed consent will emphasize the voluntary nature of participation.

Pregnant Women or Fetuses

 * When scientifically appropriate, briefly describe any preclinical studies (including studies on pregnant animals) and clinical studies (including studies on nonpregnant women) that have provided data for assessing potential risks to pregnant women and fetuses [45 CFR 46.204(a)]. There is no additional risk to the pregnant woman or fetus. This is a survey study to evaluate the efficacy of a structured, curriculum-based intervention to promote postinjury resilience and adjustment.
 2. * Select the condition that is applicable to this study [45 CFR 46.204(b)]: The risk to the fetus is caused solely by interventions or procedures that hold out the prospect of direct benefit for the woman or the fetus.
If there is no prospect of benefit, the risk to the fetus is not greater than minimal and the purpose of the research is the development of important biomedical knowledge which cannot be obtained by any other means.
 * Provide protocol-specific information to support the selected condition above [45 CFR 46.204(b)]. Not applicable.
4. * Describe how the risk is the least possible for achieving the objectives of the research [45 CFR 46.204(c)]. There is no additional risk to the pregnant woman or fetus. This is a survey study to evaluate the efficacy of a structured, curriculum-based intervention to promote postinjury resilience and adjustment.
 5. * Describe how consent will be obtained from the pregnant woman if the research may: directly benefit the pregnant woman, directly benefit the pregnant woman and the fetus, or offer no benefit for the woman nor the fetus (when risk to the fetus is not greater than minimal) and the purpose of the research is the development of important biomedical knowledge that cannot be obtained by any other means [45 CFR 46.204(d)]. Not applicable.
6. If the research may directly benefit the fetus only, describe how the consent of the pregnant woman and the father will be obtained. [45 CFR 46.204(e)]\
Note: The father's consent is not required if he is unable to consent because he is unavailable, incompetent, temporarily incapacitated, or the pregnancy resulted from rape or incest.

Not applicable.

- 7. * Describe how each individual providing consent is fully informed regarding the reasonably foreseeable impact of the research on the fetus or neonate [45 CFR 46.204(f)]. There is no additional risk to the pregnant woman or fetus. This is a survey study to evaluate the efficacy of a structured, curriculum-based intervention to promote postinjury resilience and adjustment.
- 8. For children who are pregnant, describe how you will obtain assent from the child and permission from the parent(s) of the pregnant child [45 CFR 46.204(g)]. Not applicable.
- 9. * Will inducements, monetary or otherwise, be offered to terminate a pregnancy [45 CFR 46.204(h)]?

- No
- 10. * Will individuals engaged in the research have any part in any decisions as to the timing, method, or procedures used to terminate a pregnancy [45 CFR 46.204(i)]?

11. * Will individuals engaged in the research have any part in determining the viability of a neonate [45 CFR 46.204(j)]?

Decisionally Impaired Adults

1. * Choose the nature of the decisional impairment participants will have:

Temporarily Incompetent to Give Consent

Permanently Incompetent to Give Consent

2. * Explain why this population is necessary for the conduct of the study.

The purpose of the study is to evaluate the efficacy of a structured, curriculum-based intervention to promote postinjury resilience and adjustment. TBI often causes physical and mental disabilities. Thus, adults with physical and/or mental disabilities are included.

3. * Describe methods for determining whether participants are capable of providing consent or assent.

In any case where the research staff have concerns about the individual's ability to provide informed consent, formal assessment of decision-making capacity is made using the MacArthur Competence Assessment Tool, Clinical Research version (MacCAT-CR). This is a second-generation instrument based on pioneering multicenter studies of treatment capacity (Appelbaum, 1995). It has excellent content validity, and is the only current instrument that assesses the full range of abilities relevant to capacity for giving informed consent to participate in research ([name], 2001). It has previously been used in persons with schizophrenia (Carpenter, 2000), depression (Appelbaum, 1999), and dementia ([name], 2001). Minimum values on each scale of the MacCAT-CR are established as two standard deviations below the norms of competent persons from the community, which have previously been published. ([name], 2001) Such an approach is commonly used in assessment of decision-making capacity (Grisso, 1995; Grisso, 1998; Marson, 1995) and has been shown to be more stringent than expert assessment of capacity ([name], 2001). It generally requires 15 to 20 minutes to administer and is easily learned by investigators (Appelbaum, 1999; [name], 2001).

